Protocol Cover Page for clinicaltrials.gov

Clinical Trial of the On-X[®] Valve Using Low Dose Anticoagulation

(also known as PROACT: Prospective Randomized On-X Anticoagulation Clinical Trial)

NCT00291525

Study Protocol - Rev. N, March 3, 2014

Investigational Plan

Clinical Trial of the On-X[®] Valve Using Low Dose Anticoagulation

[name] On-X Life Technologies, Inc.

> 2005-01, Rev. N, March 3, 2014 MVR Arm Late Enrollment Only

Clinical Trial of the On-X[®] Valve Using Low Dose Anticoagulation

Table of Contents

			Pages
I.	Hypothes		
II.	Study De	1	
	A. Pa	tient Inclusion	1
	B. Pa	atient Exclusion	1
	C. Te	est and Control Group Drug Therapies	3
	D. Sa	ample Size	3
	E. Ce	enter Participation	6
	F. St	udy Responsibilities	7
III.	Patient Follow-up		9
	A. Ei	ndpoints	9
	B. Fo	bllow-up Regime and Intervals	10
	C. In	vestigational Procedures	10
	D. Ec	chocardiography Procedures	22
	E. Ez	xplant Procedures	23
	F. A	dverse Events	24
	G. St	udy Review	24
	H. Da	ata Analysis	25
	I. Re	eports	25
IV.	Device Description and Risk Analysis		25
V.	Monitoring Procedures		27
VI.	Legal/Ethical Considerations		29
VII.	References		30

- Appendix A Case Report Forms
- Appendix B Investigators Agreement
- Appendix C Example Informed Consent
- Appendix D Labeling
- Appendix E IRB and Investigator Information
- Appendix F Echocardiography Procedures

Clinical Trial of the On-X[®] Valve Using Low Dose Anticoagulation

I. Hypothesis

Various patient groups with the On-X Valve can be maintained safely on lower doses of Coumadin[®] or on antiplatelet drugs only rather than the standard dose of Coumadin and aspirin presently recommended by ACC/AHA or ACCP professional societies.

II. Study Design

This is a longitudinal, randomized (randomization to occur at the 3 month follow-up) study comparing the On-X valve on low dose anticoagulation (test group) to concomitant control groups of On-X valves receiving standard Coumadin/aspirin therapy, and also to FDA objective performance criteria (OPC)^[1]. It is a multicenter study consisting of up to 50 centers in the United States, Canada and Italy enrolling and randomizing no more than 1200 patients as described in Section II.D. A list of participating centers is included in Appendix E with updates available upon request or as required by the FDA approval order.

A. Patient Inclusion

- 1. Patients requiring isolated aortic valve replacement (AVR), or isolated mitral valve replacement (MVR).
- 2. AVR patients receiving low dose or antiplatelet only anticoagulation will be divided into groups at low risk and high risk for thromboembolism with all patients being in the low risk group except for patients with the following conditions which place a patient in the high risk group:

Chronic atrial fibrillation (see definition below) Left ventricular ejection fraction < 30 % Enlarged left atrium >50mm diameter Spontaneous echo contrasts in the left atrium Vascular pathology (see definition below) Neurological events (see definition below) Hypercoagulability (see definition below) Left or right ventricular aneurysm Lack of platelet response to aspirin or clopidogrel (see definition below)

Women receiving estrogen replacement therapy

- 3. Concomitant cardiac surgery is allowed
- 4. Adult patients
- B. Patient Exclusion
 - 1. Right side valve replacement
 - 2. Double (aortic plus mitral) valve replacement
 - 3. Patients with active endocarditis at the time of implant

- 4. Previous confirmed or suspected thromboembolic event or thrombophlebitis occurring or resolving within the last year prior to enrollment
- 5. Other terminal illness
- 6. Patients who are in an emergency state
- 7. Inability to return for required follow-ups
- 8. Patients with an On-X valve implanted within the study and subsequently explanted
- 9. Patients who are known to be pregnant, plan to become pregnant or are lactating
- 10. Patients with acquired immunodeficiency syndrome or know to be HIV positive
- 11. Patients who are prison inmates or known drug or alcohol abusers
- 12. Patients unable to give adequate informed consent.

All patients meeting the criteria will be invited to participate.

Definitions -

Anticoagulation or anticoagulant -

For the purposes of this study anticoagulation shall mean any drug therapy that interferes with the coagulation of the blood whether by inhibition of vitamin K (Coumadin) or inhibition of platelet aggregation (aspirin or clopidogrel). Anticoagulant regime shall be specified whenever discussed.

Chronic Atrial Fibrillation –

Atrial fibrillation that is unresponsive to medical or cardioversion therapy and that has become the primary heart rhythm of the patient, also called persistent atrial fibrillation, having been present in the patient for at least 1 month.

Hypercoagulability -

Hypercoagulability in AVR patients will be defined by the following blood tests and results done preoperatively with the patient not on Coumadin:

- 1. APC resistance (Factor-V-Leiden mutation) heterozygous or homozygous
- 2. Prothrombin mutation heterozygous or homozygous
- 3. AT-III activity below normal
- 4. Protein C activity below normal
- 5. Protein S activity below normal
- 6. Factor VIII activity elevated above 250%.
- 7. Lipoprotein above normal

Antiplatelet Resistance (Treatment Failure) -

Resistance to aspirin or clopidogrel in AVR patients will be defined by clinical laboratory tests and results done preoperatively or postoperatively after patients have been taking aspirin and clopidogrel for at least 1 week (see section III C page 12 for enrollment processes):

- 1. Urine 11 dehydro thromboxane B2 not reduced after aspirin treatment
- 2. P2Y 12 not reduced

Vascular Pathology -

For the purposes of determining AVR risk in this study, vascular pathology shall include any historical evidence of carotid or peripheral artery occlusion of at least 50% by ultrasound or angiography, arterial aneurysms, claudication and/or ischemic ulcers of the lower extremities.

Neurological events -

For the purposes of determining AVR risk in this study, neurological events shall include any historical evidence of transient ischemic attack (TIA), stroke or cerebral aneurysm.

C. Test and Control Group Drug Therapies

Isolated Aortic Valve Replacement -

Test Group I (high risk AVR) – First 3-months postoperation, Coumadin at an INR target of 2.0 to 3.0 with 81 mg/day aspirin will be used. After 3-months, Coumadin dose will be reduced to an INR target of 1.5 to 2.0 with 81 mg/day of aspirin continued. Enrollment in this arm has ceased.

Test Group II (low risk AVR) – First 3-months postoperation, Coumadin at an INR target of 2.0 to 3.0 with 81 mg/day aspirin will be used. After 3-months, Coumadin dose will be removed and clopidogrel will be added using a loading dose of 300 mg followed by 75 mg/day with aspirin at 325 mg/day. AVR low risk patients who do not pass hypercoagulability or drug response tests will no longer be moved to the high risk group. This arm has been closed. See Addendum A for close out process for this test group and its control.

Control Groups – Postoperatively Coumadin with an INR target of 2.0 to 3.0 with 81 mg/day aspirin throughout the study. A separate control group will be used for each test group above.

Mitral Valve Replacement -

Test Group III, (regardless of risk) – First 3-months postoperation, Coumadin at an INR target of 2.5 to 3.5 with 81 mg/day (75 mg/day in Italy) aspirin will be used. After 3-months, Coumadin dose will be reduced to an INR target of 2.0 to 2.5 with 81 mg/day (75 mg/day in Italy) of aspirin continued.

Control Group – Postoperatively Coumadin with an INR target on 2.5 to 3.5 with 81 mg/day (75 mg/day in Italy) aspirin throughout the study.

D. Sample Size

A sample size estimate was conducted based on FDA OPC criteria^[1]. The study is expected to test the safety of low dose (LD) therapy for anticoagulant therapy in On-X valve patients with LD therapy consisting of the use of Coumadin in combination with aspirin or the use of antiplatelet therapy alone. This study is designed as a non-inferiority study requiring only that LD therapy is not inferior to standard

Coumadin/aspirin treatment. Testing the superiority of LD therapy with adverse event rates as low as expected would require exposure of a prohibitively large patient group. It was necessary for the sample size calculation to assume an acceptable event rate for the primary endpoints of thromboembolism, thrombosis and bleeding events derived by summing the FDA OPC's. The incident rate of the sum of these three events needs to be at least as low as the OPC sum, 7.3%. Table 1 gives the resulting sample size requirements based on a variety of outcomes.

The number of patients to be enrolled in the clinical trial is based first on the ability to show that linearized adverse event rates for the primary endpoints in the test groups are not inferior to the corresponding control groups and second on the ability to show that all valve related adverse event rates in the test groups do not equal or exceed 2 times the rates determined to be acceptable for mechanical valves.

For the first criterion above, the test group will need to have less than 6%/ptyr cumulative rate of the three events for the study to reach significance with a randomized patient population of between 150 and 250 per group followed for between 5 and 6.7 years at a statistical power of 80% with type I error of 0.05 and a maximum allowable difference between groups of 1.5%. It is expected that each of 50 centers will be able to enroll an average of 30 patients into the study balanced to provide adequate population in each sub-group, providing sufficient patient-years to test the hypothesis, which under the above conditions is around 1000 as shown in Table 1. Thus the study has 200 patients per group in AVR high risk with an average of 5 years of follow-up, or alternatively 150 patients in AVR low risk averaging 6.7 years of follow-up and and up to 250 MVR averaging 4 years of follow-up, providing the approximately 1000 patient-years per group estimated to meet hypothesis.

For the second criterion above, the established rates are the objective performance criteria (OPC) given in the FDA guidance document ⁽¹⁾. The adverse event rates for which OPCs are established include the primary endpoints of thrombosis, thromboembolism and bleeding and the secondary endpoints of paravalvular leak and endocarditis as listed below:

% per valve year (R_A)
0.8
3.0
3.5
1.5
1.2
1.2

In the comparison to OPCs for each adverse event, the null hypothesis being tested is that the true adverse event rate for each test group is equal to or greater than twice the acceptable rate. Rejecting the null hypothesis would conclude that the rate for the test groups is less than two times the acceptable rate. The null and alternative hypotheses can be written as:

Null hypothesis:	$R \ge 2R_A$
Alternative hypothesis:	$R < 2R_A$

Table 1

Sample Size Estimation for On-X Trial LD Therapy vs. Control

The sample size estimation is based on one-sided proportion test, which tests that the incidence rate of thrombosis, thromboembolism and hemorrhage in the LD therapy groups are at least as low as the control groups.

				Maximum Allowable	
Type I Error	Statistical	Expected	Expected	Difference	Needed
(One-sided	Power	Proportion	Proportion	between Two Groups	Patient
Test)		In Control	In Low Dose	to Declare Non-inferiority	Years
		Group	Group		
0.05	80%	7.3%	4.5%	2.0%	309
			5.0%	2.0%	398
			6.0%	2.0%	719
			7.3%	2.0%	2112
			4.5%	1.5%	381
			5.0%	1.5%	504
			6.0%	1.5%	992
			7.3%	1.5%	3739
			4.5%	1.0%	483
			5.0%	1.0%	663
			6.0%	1.0%	1461
			7.3%	1.0%	8388
0.025	80%	7.3%	4.5%	2.0%	393
			5.0%	2.0%	506
			6.0%	2.0%	914
			7.3%	2.0%	2682
			4.5%	1.5%	484
			5.0%	1.5%	641
			6.0%	1.5%	1260
			7.3%	1.5%	4748
			4.5%	1.0%	613
			5.0%	1.0%	842
			6.0%	1.0%	1856
			7.3%	1.0%	10650

Where R is the observed event rate and R_A is the corresponding OPC. FDA's guidance document estimates that 800 patient years are required to test this hypothesis assuming 95% confidence, 80% power and an annual attrition of 5%. This amount of trial experience is consistent with the requirements of the first criterion shown in Table 1 indicating that a patient group of 200 followed for 5 years average or 150 followed for 6.7 years average will be adequate for both purposes.

E. Center Participation

The principal investigators selected will be responsible for fulfilling the clinical trial requirements that are outlined in this investigational plan. The investigational center should have the necessary resources to allow the investigator to adhere to all clinical trial requirements. The following criteria will be used to select centers and investigators for participation in this clinical trial:

- Expertise in clinical areas relevant to the On-X heart valve LD therapy clinical trial. This includes an extensive background in cardiovascular surgery and management of patients with prosthetic heart valves, and prior experience in conducting clinical studies on prosthetic heart valves.
- Appropriate and sufficient personnel should be available to obtain and report data as required by the investigational plan. There should be an investigational group at each center consisting of at least: the investigator (a cardiovascular surgeon); co-investigators, who will also implant the study valve; and a center study coordinator to manage, organize and coordinate the routine activities of the clinical trial.
- Appropriate and sufficient patient population should be available to meet the implant schedule requirements for aortic and mitral prostheses.
- Access to a hospital and/or clinic having the equipment necessary to perform the clinical trial.
- Willingness to comply with all aspects of the clinical trial as described in the investigational plan. This includes collection of complete and accurate data in a timely manner according to the prescribed patient follow-up schedule. Additionally, investigators should be accessible to their support staff, and sponsor and monitor personnel.

A visit by the sponsor and/or monitor will be scheduled with the investigator and members of the investigational group to provide in-depth training and discussion of the investigational plan and clinical trial requirements prior to the first implant.

Topics to be covered at the pre-study visit will include:

- Review of the study protocol requirements particularly patient selection and informed consent;
- Review of proper data management;
- Review of follow-up requirements and monitoring procedures;

- Review of anticoagulant regime;
- Review of complication definitions and reporting;
- Review of explant procedures; and
- Review of reporting requirements.
- F. Study Responsibilities (Records And Reports)

Sponsor –

The sponsor shall be responsible for the following activities:

- a) selection and training of investigators;
- b) ensuring that all information within the study is properly distributed;
- c) providing all study materials, such as preclinical data and documentation, valves, case report forms, etc.;
- d) obtaining and keeping records of all approvals, and agreements;
- e) selection of monitors;
- f) ensuring that provisions for compensation in the event of injury are made;
- g) ensuring compliance (through the monitor) with the investigational plan;
- h) maintaining all correspondence pertaining to the investigation;
- i) obtaining, keeping and reporting adverse device effects per the protocol and all rules and regulations;
- j) reporting any approval withdrawals, and if necessary, terminating the study;
- k) keeping a current investigator list;
- 1) filing appropriate progress and final reports; and
- m) reporting any failure to obtain prior informed consent.

Monitor -

The monitor shall be responsible for the following activities:

- a) secure compliance with the investigational plan;
- b) evaluate and report adverse effects (expected or unanticipated);
- c) if necessary, assist in termination of the study;
- d) identify protocol deviations or problems;
- e) audit data from case reports;
- f) confirm informed consent;

- g) help train centers in conduct of the study;
- h) maintain sponsor to investigator communications;
- i) determine cause of plan deviations and work to remedy those deviations; and
- j) document any patient withdrawals.

The monitor must establish a good working relationship with the administrator (study coordinator) at each clinical center.

Investigator -

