2.3 Study Endpoints

2.3.1 Safety

The primary study endpoints are the binary measures of occurrence or not of valve thrombosis, thromboembolism (TE), all major and minor bleeding events, whether or not related to drug therapy, reoperation, explant and death. The sum of all TEs (including valve thrombosis events) and major bleeding is used as the primary decision criterion for the primary endpoints.

Secondary safety study endpoints are other valve related adverse events (AEs) including the occurrence or not of endocarditis, hemolysis, hemolytic anemia, paravalvular leak and structural and non-structural dysfunction. All events shall be as defined by the AATS/STS guidelines [Akins CW, Miller DC, Turino MI, et al] for reporting valve study results.

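### Protocol II.D points to non-inferiority against control as the requirement, but leaves open what the 7.3% and twice-OPC conditions decide, and the SAP specifies none of the three as a test

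*Protocol*

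**What the plan says.** Protocol II.D (Sample Size) describes a non-inferiority design that asks only that low-dose therapy be no worse than standard therapy. SAP 4 repeats this. Around that statement stand these conditions:

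- **Sum of the three events.** "The incident rate of the sum of these three events needs to be at least as low as the OPC sum, 7.3" per cent. SAP 4 has the same sentence. In the protocol it sits between the explanation of the rate assumed for the sample size and the pointer to Table 1.
- **First criterion.** Patient numbers rest on a comparison with control: "based first on the ability to show that linearized adverse event rates for the primary endpoints in the test groups are not inferior". The margin is "a maximum allowable difference between groups of 1.5" per cent, with 80% power and type I error 0.05, one-sided in Table 1.
- **Second criterion.** Patient numbers also rest on a comparison with the OPCs: "second on the ability to show that all valve related adverse event rates in the test groups do not equal or exceed 2 times". This has written hypotheses. Under the null, each rate is at least double its OPC: "the null hypothesis being tested is that the true adverse event rate for each test group is equal to or greater than twice". For rejection, the protocol gives this reading: "Rejecting the null hypothesis would conclude that the rate for the test groups is less than two times the acceptable rate".
- **A 6% figure.** "the test group will need to have less than 6%/ptyr cumulative rate of the three events for the study to reach significance". This is the Table 1 planning rate, also worded as a need.

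SAP 2.3.1 says the sum of thromboembolism (including valve thrombosis) and major bleeding "is used as the primary decision criterion for the primary endpoints". It attaches no comparator, margin or test. SAP 9.1 compares each test group with its control by Kaplan-Meier, chi-square or Fisher tests, and relative risks with 95% intervals. SAP 6.5 makes testing two-sided unless otherwise noted. SAP 6.4 plans no multiplicity adjustment.

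**The concern.** A reader can tell that non-inferiority to control is meant to carry the study. The documents do not say what the other conditions do, or what follows when they disagree with non-inferiority. The first and second criteria are ranked as reasons for the number of patients, not as a rule for the conclusion. The SAP should turn this into a decision rule, but it contains none of the three conditions as an analysis. A relative-risk interval for a difference does not apply a margin of 1.5 percentage points.

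At stake is the claim that anticoagulation can safely be reduced in patients with a mechanical valve. If an OPC result could stand in for a failed comparison with control, a regimen worse than its randomised control could be reported as successful wherever event rates are low in both arms. If the 7.3% sentence were enforced, a regimen better than control could fail wherever both rates are high.

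**Working it through.** **Inputs.** Control 7.3%, test 6.0%, margin 1.5 points, one-sided 0.05, 80% power (Protocol II.D, Table 1). Exposure is about 1,000 patient-years per group (200 × 5; 250 × 4). The three OPCs are 0.8, 3.0 and 3.5. The row labels are lost in the extracted text, but this is the only triple of the six listed values that sums to 7.3, so it is taken as thrombosis, thromboembolism and bleeding in the order of the text.

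**1. The plan's own figure.** n = (z₀.₉₅ + z₀.₈₀)² × [p_C(1−p_C) + p_T(1−p_T)] / (margin + p_C − p_T)²
= (1.645 + 0.842)² × (0.0677 + 0.0564) / (0.015 + 0.013)² ≈ 979 patient-years per group, against 992 in Table 1 (1.3% apart). Table 1 sizes non-inferiority alone.

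**2. The three conditions as rules, at 1,000 patient-years per arm** (T and C are event counts):
- Non-inferiority: (T − C)/1000 + 1.645 × √(T + C)/1000 < 0.015.
- Twice OPC: thrombosis ≤ 9, thromboembolism ≤ 47, bleeding ≤ 56. These are the largest counts with Poisson probability ≤ 0.05 at means 16, 60 and 70.
- 7.3%: T ≤ 73. This is read as a point estimate because the documents give no test.

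**3. Example data** (thrombosis/thromboembolism/bleeding):
- A: test 8/28/34 = 7.0%, control 4.0%. The sum and all three OPC tests pass. Non-inferiority fails: 3.0 + 0.1645 × √110 = 4.73 points.
- B: test 8/30/42 = 8.0%, control 9.0%. Non-inferiority passes: −1.0 + 0.1645 × √170 = 1.14. OPC passes. The sum fails.
- C: test 17/18/20 = 5.5%, control 7.3%. Non-inferiority passes: −1.8 + 0.1645 × √128 = 0.06. The sum passes. Thrombosis fails its OPC test (upper bound 2.55 against 1.6).

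**4. Chance of success.** 400,000 simulated trials per row, Poisson counts, events split in OPC proportions:

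| Test / control, % per year | Non-inferiority | Sum ≤ 7.3 | Three OPC tests | All required | Any one enough |
|---|---|---|---|---|---|
| 6.0 / 7.3 (design) | about 78% | 96% | 87% | 70% | 99% |
| 7.3 / 7.3 | 34% | 53% | 72% | 25% | 83% |
| 8.8 / 7.3 (at the margin: 7.3 + 1.5) | 5% | 6% | 48% | 2% | 50% |

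The three conditions disagree in about 29% of trials at the design rates. At 8.8 against 7.3, nearly all of the rise from 5% to 50% comes from the OPC tests. In the other direction, with assumed rates of 10% for control and 8.5% for test, non-inferiority is met in 71% of trials and the 7.3% condition in 10%; about 61% meet non-inferiority yet miss 7.3%.

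**5. If the OPC tests were co-required.** Non-inferiority plus the three OPC tests succeeds in about 70% of trials at 7.3% against 6.0%. The criterion is worded for all valve-related events, and six OPC values are listed. For the other three (1.5, 1.2, 1.2) the same method gives cut-offs of 20, 15 and 15. The chance of passing all three is about 0.65 if true rates equal the OPCs, or 0.90 if they are scaled by 6.0/7.3. Assuming independence, 0.70 × 0.65 ≈ 46% and 0.70 × 0.90 ≈ 63%.

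**The case against.** A reader might infer that the plan sets three rival tests and never says which decides. The documents do not support that. Protocol II.D and SAP 4 both say that only non-inferiority is required, the protocol puts it first, and SAP 9.1 compares each test group with its own control. The 7.3% sentence has no hypothesis, test or confidence bound, names no arm, and stands in planning text. There are two formal criteria and one loosely worded assumption.

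A reader might also infer that the OPC criterion tolerates a sum of 14.6% (2 × 7.3%). That is the null boundary: the cut-offs cap the observed sum at 9 + 47 + 56 = 112 events, or 11.2%.

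Protocol III.G also requires termination if thrombotic and bleeding rates on low-dose therapy exceed those in the control group, among other triggers. That makes the worst outcome less likely. It is a monitoring rule, though, and does not say how the final data are judged.

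What remains is that a design asking only for non-inferiority also says the sum must meet 7.3%, and adds a fully written second hypothesis test whose role is not given. The SAP resolves neither.

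**Conclusion.** The concern holds in a limited form. Non-inferiority to the concurrent control is identifiable as the requirement. The status of the twice-OPC criterion and of the 7.3% wording is not stated, there is no rule for conflict, and no SAP analysis carries out any of the three. With a true difference exactly at the margin, false success is 5% if non-inferiority decides and about 50% if any one condition suffices. Nothing in the documents says that any one suffices; the 50% measures what the silence leaves possible.

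It would also go too far to conclude that the OPC tests must be a mandatory second hurdle. That would contradict the stated design and bring success below the planned 80%.

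The figures assume Poisson events, equal exposure of 1,000 patient-years per arm, events split in OPC proportions, and 7.3% read as a point estimate. Read on an upper 95% bound instead, example A would fail the 7.3% condition (8.54%) and B would still fail it (9.64%). The 46–63% range also assumes independence between events, which fails if any of the six listed events overlap.

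**What to change.** 1. In Protocol II.D and SAP 2.3.1, 4 and 9.1, state that the deciding test for each comparison is non-inferiority of the sum to its concurrent randomised control, with the 1.5-point margin at the planned one-sided 0.05. Define the sum in the same place: SAP 2.3.1 counts major bleeding only, whereas the primary endpoints in both documents include minor bleeding.
2. State that meeting the OPC comparison, or 7.3%, cannot replace a failed non-inferiority test. Say whether the OPC tests are supportive or co-required; either resolves the ambiguity. If co-required, no alpha adjustment is needed, but give the joint chance of success beside the 80%: about 70% for the three primary events at 7.3% against 6.0%, and lower if all six listed OPC values count.
3. In Protocol II.D and SAP 4, reword the 7.3% sentence to say that the control rate is assumed to be 7.3%, the OPC sum.

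The cost is wording in both documents. The stated chance of success becomes less favourable only if the sponsor makes the OPC tests co-required.

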4. SAMPLE SIZE CONSIDERATIONS

The study is expected to test the safety of low dose (LD) therapy for anticoagulant therapy in On-X valve patients with LD therapy consisting of the use of Coumadin® in combination with aspirin or the use of antiplatelet therapy alone. The sample size for this study was designed as a non-inferiority study requiring only that LD therapy is not inferior to standard Coumadin®/aspirin treatment. It was necessary for the sample size calculation to assume an acceptable event rate for the primary endpoints of thromboembolism, thrombosis and bleeding events derived by summing the FDA OPC's. The incident rate of the sum of these three events needs to be at least as low as the OPC sum, 7.3%.

The test group will need to have less than 6%/ptyr cumulative rate of the three events for the study to reach significance with a patient population of 200 per group followed for 5 years at a statistical power of 80% with type I error of 0.05 and a maximum allowable difference between groups of 1.5%.

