6.5 Significance Level

Unless otherwise noted, all statistical analyses will be conducted with a significance level (α) of 0.05 and utilize two-sided testing.

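### Protocol II.D and SAP 4 give 6%/pt-yr as the rate needed for significance, but it is the assumed true low-dose rate, not the non-inferiority limit

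*Protocol*

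**What the plan says.** Protocol II.D describes the aim as "This study is designed as a non-inferiority study requiring only that LD therapy is not inferior to standard" Coumadin/aspirin treatment. Its first criterion compares primary-endpoint rates in each test group with those in the corresponding control group.

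For that criterion it says that "the test group will need to have less than 6%/ptyr cumulative rate of the three events for the study to reach significance". The sentence goes on to give 150 to 250 patients per group followed for 5 to 6.7 years, "at a statistical power of 80% with type I error of 0.05" and "a maximum allowable difference between groups of 1.5"%. SAP 4 repeats it: "The test group will need to have less than 6%/ptyr cumulative rate of the three events for the study to reach significance", with 200 patients per group, 5 years, and the same power, type I error and margin.

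Table 1 of the Protocol says that "The sample size estimation is based on one-sided proportion test". The row for control 7.3%, low dose 6.0%, margin 1.5%, one-sided 0.05 and 80% power gives 992 patient-years. There, 6.0% stands in the column of expected low-dose proportions. The row with both rates at 7.3% and the same margin gives 3739. The SAP does not reproduce Table 1.

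SAP 6.5 says that, unless otherwise noted, analyses are "conducted with a significance level (α) of 0.05 and utilize two-sided testing".

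**The concern.** A non-inferiority comparison with a concurrent control succeeds or fails on the observed difference and its standard error. It has no fixed test-group rate at which it becomes significant. The sentence turns a planning assumption about the true LD rate into a condition that the test group must meet.

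This matters most in the SAP. Section 4 is the only place there that gives a success figure or the 1.5-point margin. SAP 9.1 lists Kaplan-Meier comparisons, chi-square or Fisher tests, and relative risks with 95% intervals, with no margin and no bound to compare with it. A reader who wants the success rule would find the 6% figure, and could then reject a result that meets the margin or accept one that fails it.

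The sentence also leaves unsaid that its 80% power depends on LD being better than control, although the stated aim is only that LD be no worse.

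**Working it through.** **Inputs.** Planned control rate 7.3% (OPC sum; Table 1). Assumed true LD rate 6.0% (Table 1). Margin 1.5 points, one-sided 0.05 and 80% power (Protocol II.D). Exposure of about 1000 patient-years per group, from 200 × 5 = 1000, 150 × 6.7 = 1005 or 250 × 4 = 1000 (Protocol II.D). Equal allocation (SAP 3.1). Like Table 1, the check treats patient-years as the units of a proportion test. The documents assume no control rate other than 7.3%; the values 6.0% and 5.0% below are my illustrations.

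**Step 1: reproduce Table 1.** With pC for control and pT for low dose,

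n = (1.645 + 0.842)² × [pC(1−pC) + pT(1−pT)] / (margin + pC − pT)²

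- At 7.3% and 6.0%: 6.183 × (0.06767 + 0.05640) / 0.028² = 979, against 992 stated (1.3% apart). A Poisson variance gives 1049.
- At 7.3% and 7.3%: 6.183 × 0.13534 / 0.015² = 3719, against 3739 stated.

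So 6.0% enters the calculation as the true LD rate under the alternative.

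**Step 2: the actual limit.** Non-inferiority is shown when

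pT − pC + z × √{[pC(1−pC) + pT(1−pT)] / 1000} < 0.015, with observed rates.

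Solving for the largest pT:

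| Observed control | Limit, one-sided 0.05 (z = 1.645) | Limit, two-sided 0.05 (z = 1.960) |
|---|---|---|
| 7.3% | 6.91% | 6.57% |
| 6.0% | 5.77% | 5.46% |
| 5.0% | 4.90% | 4.62% |

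At control 7.3%, one-sided, a Poisson variance gives 6.84% and a Farrington-Manning score test 6.90%. The limit equals 6% only when observed control is about 6.26% (Poisson 6.33%), or about 6.63% under the two-sided rule.

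**Step 3: examples, upper one-sided 95% bound.**

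- LD 6.5%, control 7.3%: −0.8 + 1.645 × 1.133 = 1.06 points. It passes, although 6.5% is above 6%.
- LD 6.0%, control 6.0%: 0 + 1.645 × 1.062 = 1.75 points. It fails.
- LD 5.9%, control 5.0%: 0.9 + 1.645 × 1.015 = 2.57 points. It fails, although 5.9% is below 6%.

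**Step 4: power at 1000 patient-years, one-sided 0.05.** Power = Φ[(0.015 + pC − pT)/SE − 1.645].

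- True rates 7.3% and 6.0%: Φ(0.028/0.01114 − 1.645) = Φ(0.869) = 81%.
- True rates 7.3% and 7.3%: Φ(0.015/0.01163 − 1.645) = Φ(−0.356) = 36%.

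**Step 5: sensitivity to exposure.** The sentence's own ranges run from 150 × 5 = 750 to 250 × 6.7 = 1675 patient-years. Over that range the one-sided limit at control 7.3% runs from 6.64% to 7.32%.

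**The case against.** The sentence should be read to its end. It goes on to 80% power, a type I error and a margin, and the next sentence of the Protocol points to Table 1, where 6.0% is plainly an expected proportion. Read that way it is a loosely worded power statement, and that is probably what was meant. No analysis section applies 6% as a decision rule. Table 1 prints the equal-rates row beside the chosen one, so a Protocol reader can see that about 1000 patient-years falls well short of 3739.

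Most of this stands. It limits the defect to wording but does not remove it. The words still set a condition for significance, both documents carry them, and the SAP gives neither Table 1 nor another success rule.

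Four stronger readings are tempting, and the documents do not support them.

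- *The sample size is wrong.* It is not: 992 reproduces within 3%.
- *The 80% is false because a true rate of 6.0% gives an observed rate below 6% only about 48% of the time.* Neither document says that 80% is the chance of observing a rate below 6%.
- *6% is too lenient whenever control falls short of 7.3%.* Between about 6.3% and 7.3% it is still too strict.
- *No absolute rate applies to the test group.* Both documents also say: "The incident rate of the sum of these three events needs to be at least as low as the OPC sum, 7.3"%. The second criterion separately requires each test-group event rate to be below twice its OPC.

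**Conclusion.** The concern holds as a misstatement of the success rule for the first criterion, in both documents. At an observed control rate of 7.3%, the stated 6% is about 0.9 point stricter than the margin requires (one-sided 0.05), or about 0.6 point under the two-sided rule. At an observed control rate of 5.0% it is about 1.1 points too lenient, one-sided. The changeover is at an observed control rate of about 6.3%, one-sided.

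The stated power rests on LD being truly 1.3 points better than control. If the true rates are equal at 7.3%, power is about 36%. Failure to show non-inferiority would then be the more likely outcome, and would not by itself show that LD is worse.

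The figures assume about 1000 patient-years per group, equal allocation and a normal approximation. The Poisson and score-test checks move the 7.3% limit by less than 0.1 point.

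**What to change.** Replace the sentence in Protocol II.D and SAP 4 with:

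> Assuming true rates of 7.3% (control) and 6.0% (LD), about 1000 patient-years per group give 80% power, at one-sided alpha 0.05, to show that the upper one-sided 95% confidence bound for LD minus control is below 1.5%/pt-yr, which is the success rule for the first criterion; at equal true rates of 7.3% the power is about 36%.

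State in the SAP that this one-sided bound is the exception to the two-sided rule in 6.5. Without that exception, 1000 patient-years give 71% power at 7.3% and 6.0%, and Table 1 asks for 1260 at one-sided 0.025.

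Do not put a fixed observed limit such as 6.9% in place of 6%, because it would hold for only one control rate and exposure. Leave the OPC sentence and the second criterion as they are.

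The cost is one sentence in each document and a line in SAP 6.5. Enrolment, follow-up and treatment do not change. The documents would then say openly that the stated power depends on LD being better than control.
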